CGM data will be analyzed for mean blood glucose values, time spent in hyperglycemic (>240, >300mg/dl) and hypoglycemic (<50, <70, <80 mg/dl) ranges and various indices of glycemic variability. Laboratory analysis for A1C will be performed at baseline, monthly thereafter during the pregnancy, and post-partum. Routine blood tests will be performed in all subjects in each trimester (see Table 1).

Primary outcomes will be:

- 1) Glucose variability as measured by glucose excursions from self-monitoring blood glucose (SMBG) data through log books and downloads as well as CGM downloads and various indices [J-index, mean amplitude of glycemic excursion (MAGE), high blood glucose index (HBGI), low blood glucose index (LBGI)] from CGM downloads.
- 2) Changes detected by the hypoglycemia fear questionnaire.

Secondary outcomes will be:

- 1) How CGM alone and CGM with Share™ usage affect A1C compared to no CGM use,
- 2) Progression of diabetes complications (retinopathy, nephropathy),
- 3) Maternal and fetal outcomes (eclampsia/pre-eclampsia, live birth rates, birth weight, neonatal hypoglycemia, and other similar measures).

Introduction:

Among the US population, 29.1 million people (9.3%) have diabetes (1). Pre-existing diabetes has to be managed very carefully throughout pregnancy to optimize maternal and fetal outcomes (2). Among women

with T1DM who are pregnant, the tools that we have to regulate maternal glucose control include multiple daily injections (MDI), continuous subcutaneous insulin infusion therapy (CSII) also known as insulin pump therapy, and for high-risk individuals continuous glucose monitoring (CGM) (2). CGM use in pregnancy has been shown to be safe, to reduce the frequency of severe hypoglycemia, and to improve A1C values (3-6). Sensor-augmented pump therapy with CGM use continuously was shown to lower A1C more than intermittent use in pregnant women with T1DM (7). However, few studies have measured changes in glucose variability that occur with CGM use during pregnancy and no studies have evaluated how tools that allow family and friends (followers) to access glucose trends affect outcomes during pregnancy.

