Visits 3 through 13 (Weeks 5 to 40):

Subjects will come to the BDC for routine clinical care at least once per month for the duration of the pregnancy (through gestational week 40, though some women deliver up to 42 weeks gestation) and for continued study participation. Per routine clinical care, we will screen for diabetic neuropathy on physical exam, thyroid disease (TSH blood draw), and kidney disease (24-hour urine protein with creatinine) at least once each trimester. Also per routine clinical care, women will be asked to get a dilated retinal eye exam each trimester and to provide the BDC with a copy of the provider's report of each exam.

Subjects in Groups 1 and 2 will receive 4 new sensors per month, but may choose to get 2 sensors twice a month instead, at study visits. Use of acetaminophen-containing medications like Tylenol® during sensor wear may affect device performance, therefore we will ask subjects to keep a log of each time these medications are used. We will ask subjects at each monthly visit whether she used acetaminophen-containing medications during the previous month and when. Followers will be administered a brief questionnaire at the beginning of every month inquiring on the frequency of low alerts, high alerts, viewing glucose trends, and actions they may have taken on behalf of the subjects because of the above (see Table 2 and *Follower Questionnaire* for details). On source documents, we will also record how often subjects required an intervention for low or high glucose values within the previous month, and the nature of the interventions. If in Group 2, we will keep source documentation about interventions resulting from a Share™ alert within the previous month.

Data on all pregnant subjects for medications, vital signs, height/weight, insulin doses, glucometer downloads, insulin pump downloads (if applicable), and CGM downloads (if applicable) will be collected at least once per month and as often as every week. All subjects will be asked to collect a 7-point profile for SMBG measurements (blood glucose measurements before meals, 2 hours after meals, and at bedtime) along with meal insulin dosing for 1 week once per trimester (see SMBG Questionnaire). A1C will be measured once per month. Subjects will be asked about updated concomitant drugs and any AEs that may have occurred. Each subject will be given a hypoglycemic fear questionnaire.

Visit 14 (Weeks 44 to 52):

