The primary endpoints are glucose variability and changes detected by hypoglycemic fear survey. We will measure indices of glucose variability (mean glucose \pm SD, % of glucose within/above/below target ranges, J Index, High Blood Glucose Index [HBGI], Low Blood Glucose Index [LBGI], Mean Amplitude of Glycemic Excursions [MAGE], CONGA_n) throughout pregnancy using the SMBG 7-point profiles for one week taken once per trimester. Hypoglycemic fear survey results will be assessed once monthly over the pregnancy. We will compare outcomes within individuals over time and between individuals of the different study arms. We will test whether outcomes differ between women using Dexcom alone and women using Dexcom with Share™ using interaction terms, and will stratify analyses if differences by group are greater than 10 mg/dL in mean glucose levels are detected. Since SMBG logs will be taken at multiple time points over the pregnancy and since CGMs will be worn continuously for the duration of each pregnancy, linear mixed models will be used to assess changes in outcome measures (GV, time spent in target below or above target) over time in each trimester of pregnancy. We will use linear mixed models to assess changes in the hypoglycemic fear survey in each month of the pregnancy. Secondary endpoints include A1C differences among study arms. Improvement in glycemic variability parameters with a possible reduction of A1C by 0.3%, measured as the difference of the mean A1C laboratory values of the arms of the study between baseline (0-3 months, first trimester), second trimester (3-6 months), and third trimester (6 to 9 months). Mixed models account for missing data, allow for an unstructured covariance matrix for repeated measures, and account for inter-subjects correlation of measurements. Secondary outcomes will be used

in the same mixed models. Differences in frequency of low alert glucose rates, high alert glucose rates, and interventions for low or high glucose values among the followers for each study arm will be analyzed with student t-tests. A p-value < 0.05 will be considered significant, and we will perform statistical analyses with SAS software (version 9.3, SAS Institute, Cary NC).

Publication Strategy:

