Appendix D

SMBG (Self-Monitoring Blood Glucose) Questionnaire

Subject ID: _____

Clinic Visit: (dd/mmm/yyyy) : _____ / _____ / _____

Gestational Age: 8 to 12 weeks 20 to 24 weeks 32 to 36 weeks Post-Partum

DAY	DATE	TIME POINT	BLOOD GLUCOSE BEFORE MEAL (OR BEDTIME)	SHORT-ACTING INSULIN DOSE (UNITS)	BLOOD GLUCOSE 2 HOURS AFTER MEAL
1		Breakfast			
		Lunch			
		Dinner			
		Bedtime			
2		Breakfast			
		Lunch			
		Dinner			
		Bedtime			
3		Breakfast			
		Lunch			
		Dinner			
		Bedtime			
4		Breakfast			
		Lunch			
		Dinner			
		Bedtime			
5		Breakfast			
		Lunch			
		Dinner			
		Bedtime			
6		Breakfast			
		Lunch			
		Dinner			
		Bedtime			
7		Breakfast			
		Lunch			
		Dinner			
		Bedtime			

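### The SAP takes CONGA_n and MAGE from 7-point fingerstick profiles, which cannot yield CONGA_n in its usual sense and give a MAGE not interchangeable with the CGM-based MAGE in the outcome list

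*Combined protocol and SAP*

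**What the plan says.** The Statistical Analysis Plan makes glucose variability one of two primary endpoints. It lists the indices in one sentence: mean and SD, percentages within, above and below target, J-index, HBGI, LBGI, MAGE and CONGA_n. The sentence ends by naming the source: "Mean Amplitude of Glycemic Excursions [MAGE], CONGA_n) throughout pregnancy using the SMBG 7-point profiles for one week taken once per trimester". It gives no value for n and no rule for MAGE.

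The profile is described under Visits 3 through 13: "blood glucose measurements before meals, 2 hours after meals, and at bedtime) along with meal insulin dosing for 1 week once per trimester". The recording form is Appendix D. Each day has four rows (breakfast, lunch, dinner, bedtime), a date, an insulin dose and two glucose columns, headed "BLOOD GLUCOSE BEFORE MEAL (OR BEDTIME)" and "BLOOD GLUCOSE 2 HOURS AFTER MEAL". There is no column for clock time and no overnight row.

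The primary outcomes list in the opening summary names a different source. It uses "self-monitoring blood glucose (SMBG) data through log books and downloads", together with CGM downloads, for excursions. It then takes the J-index, MAGE, HBGI and "low blood glucose index (LBGI)] from CGM downloads". CONGA_n is not in that list.

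CGM data are collected in any case: under Visits 3 through 13, "glucometer downloads, insulin pump downloads (if applicable), and CGM downloads (if applicable) will be collected at least once per month". Group 3 does not wear CGM.

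**The concern.** Both indices describe how glucose moves through time. CONGA_n needs readings a known number of hours apart across the record. MAGE needs the peaks and troughs. A form with seven meal-anchored values a day, no times and nothing overnight does not supply the first and supplies the second only in part.

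An analyst who follows the SAP sentence literally would have to drop CONGA_n or report something else under its name. For MAGE, two analysts working from two sections of the same document would produce different quantities with one label. The choice also interacts with the design: CGM data give no MAGE or CONGA_n for the no-CGM arm, while SMBG data give an index that is not equivalent. If the source is settled after the data are seen, so is the content of a primary endpoint.

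**Working it through.** **Definitions used.** The documents define neither index, so I assume the usual ones. CONGA_n is the SD of the differences G(t) − G(t − n hours) over all t in a continuous record. MAGE is the mean size of the peak-to-trough excursions that exceed a threshold.

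**1. The plan's own figure.** From Appendix D: 3 pre-meal + 3 post-meal + 1 bedtime = 7 values a day, and 7 × 7 = 49 a week. This reproduces the 7-point profile.

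**2. Lags that the form guarantees.** The only fixed interval is from before a meal to the nominal 2 hours after it: 3 pairs a day, 3 × 7 = 21 a week. All other intervals depend on when the woman ate and went to bed, which the form does not record.

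**3. What a typical day would give if times were known (assumed schedules).**

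| Meals; bedtime (h) | Gaps between values (h) | Overnight gap | 1-h pairs | 2-h pairs | 4-h pairs | 6-h pairs |
|---|---|---|---|---|---|---|
| 7, 12, 18; 22 | 2, 3, 2, 4, 2, 2 | 9 h | 0 | 4 | 2 | 2 |
| 6, 11.5, 17.5; 21 | 2, 3.5, 2, 4, 2, 1.5 | 9 h | 0 | 3 | 1 | 2 |

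The 4-hour and 6-hour pairs, and the fourth 2-hour pair in the first row, arise by chance of the schedule and could not be identified from the form. On either schedule 9/24 = 37.5% of the day has no value.

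**4. The same count on CGM.** The documents do not give the sampling interval; I assume 5 to 15 minutes. Pairs in 24 hours = readings per day − n × 60 / interval.

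| n | 5 min (1440/5 = 288 readings) | 15 min (1440/15 = 96 readings) | Appendix D, guaranteed |
|---|---|---|---|
| 1 | 288 − 12 = 276 | 96 − 4 = 92 | 0 |
| 2 | 288 − 24 = 264 | 96 − 8 = 88 | 3 |
| 4 | 288 − 48 = 240 | 96 − 16 = 80 | 0 |
| 6 | 288 − 72 = 216 | 96 − 24 = 72 | 0 |

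The 3 pairs at n = 2 are also selected: each starts at a meal and ends at its nominal 2-hour value. Their SD measures the spread of meal increments. It is not the SD of 2-hour changes over day and night.

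**5. MAGE.** Seven values give at most 7 − 1 = 6 successive differences a day. A peak is seen only if it falls at one of the seven points, and nothing is seen between bedtime and breakfast. A number can be computed, but it rests on fewer excursions than a CGM trace would show.

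**6. Sources side by side.**

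| Index | Primary outcomes list | Statistical Analysis Plan |
|---|---|---|
| MAGE, J-index, HBGI, LBGI | CGM downloads | SMBG 7-point profiles |
| CONGA_n | not named | SMBG 7-point profiles |

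**The case against.** The strongest reply is that the plan already takes MAGE from CGM, in the primary outcomes list, and that the SAP itself cites continuous CGM wear when it introduces mixed models for glucose variability. For MAGE this largely stands: the defect is an unreconciled source, and the remedy restores what the outcome list says. It does not help CONGA_n, which is named only in the SAP sentence. The remark on continuous wear justifies the model; it does not reassign either index.

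A second reply is that meter downloads are collected at every visit and may carry times. The documents do not say that they do, the SAP does not name them as the source for these indices, and times alone would not create regular or overnight sampling.

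Several stronger readings are tempting and are not supported:

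- A reader might infer that the profiles contain no regular lag. They do contain one, the nominal 2 hours around each meal.
- A reader might infer that MAGE cannot be computed from seven points. It can; the objection is to treating it as the same quantity as CGM MAGE.
- A reader might want a figure for how much information 7-point MAGE loses. The documents give no glucose traces, and any simulated answer would turn on how much variability is assumed to differ between women.
- A reader might infer that overnight glucose is lost to the study, or that a null result on these two indices would settle the endpoint. Groups 1 and 2 are asked to wear CGM throughout pregnancy, and the same SAP sentence lists other indices.

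Finally, barring all MAGE comparisons with Group 3 would go further than necessary. An SMBG-based MAGE, computed identically in each arm and labelled as such, is a legitimate option in a pilot.

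**Conclusion.** The point holds as a stated rule that fails for CONGA_n and conflicts with another section for MAGE. The only source the plan gives for CONGA_n yields no guaranteed pairs at n = 1, 4 or 6. At n = 2 it yields 21 meal-increment pairs a week, whose SD is not CONGA_2. MAGE from the profiles is calculable but sparser, and must not be treated as the MAGE that the outcome list takes from CGM downloads.

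This rests on the usual definitions of the two indices, since the plan supplies none. The zero and 21 counts come from the form alone; the CGM counts depend on the assumed 5 to 15 minute interval and the 9-hour overnight gap on the assumed schedules. The remaining indices in the sentence can be computed from the profiles as summaries of the sampled values. No sample-size or power figure is affected. The correction should be made before analysis, because it fixes the content of a primary endpoint.

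**What to change.** In the Statistical Analysis Plan, replace the single source clause with a source for each index:

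- **CONGA_n and MAGE:** derive from CGM downloads, with n and the MAGE algorithm and threshold stated. Analyse within and between Groups 1 and 2, on weeks that meet the 5-day capture standard given under Stratification, Visit 2. For MAGE this agrees with the primary outcomes list; add CONGA_n to that list.
- **Comparisons with Group 3:** use mean, SD, percentages within, above and below target, J-index, LBGI and HBGI, computed the same way from SMBG in every arm. The Control Arm section lists meter downloads but no 7-point profile for the chart-review women (up to 30), and says they completed none of the study questionnaires. The text should therefore state whether these comparisons use meter downloads in every arm or the profiles in prospectively enrolled women only.
- **Any SMBG-based MAGE:** label it as such, and never pool or compare it with CGM MAGE.

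The cost is wording: the CGM downloads are already collected, and no visit or measurement is added. The real loss is that CONGA_n and CGM-based MAGE cannot be compared with the no-CGM arm.

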This is a single-center, prospective, ‘open-label,’ investigator-initiated pilot study evaluating the role of continuous glucose monitor (CGM) use either alone or with remote monitoring capabilities that enable subjects to share CGM data with family and friends (whom we will call “followers” in this protocol) among women with T1DM associated with pregnancy. We hypothesize that CGM use will decrease percentage of glucose values below the target range, decrease frequency of severe hypoglycemic episodes, and increase post-prandial glucose values into the target range, with a possible reduction in A1C compared to not using CGM during pregnancy. We hypothesize that the use of remote technology (**Share™ technology**) with subject’s designated follower will decrease hypoglycemia fear and the frequency of severe hypoglycemic episodes compared to CGM use alone in pregnancy or not using CGM use in pregnancy. This study aims to improve maternal glucose management among women with T1DM with a hope to also improve health outcomes during pregnancy.

The study will enroll up to 40 patients from the Barbara Davis Center for Childhood Diabetes (BDC) Adult clinic over the age of 18 years who are pregnant (13 weeks gestation or less) or plan to become pregnant within the following 6 months. The study will also attempt to enroll up to 40 followers (one per pregnant subject) who are family members or friends of the pregnant subjects and over the age of 18 years. All subjects meeting these criteria will be invited to sign informed consent and participate in the study. All pregnant subjects will be stratified into one of three groups: (1) CGM use alone, (2) CGM use with Share™, (3) no CGM use. CGM use will be offered to all subjects, but individuals who do not want to wear a CGM will be stratified to Group 3. Stratification for Groups 1 and 2 will depend on the following: subjects and followers who have iPhones, iPads, and/or iPod touches will be placed into Group 2 which requires one of these devices to function, while all others will be placed in Group 1. All subjects will be followed for study visits with similar frequency during the pregnancy, and subjects in Groups 1 and 2 will wear the Dexcom G4 Platinum® CGM system from the first pregnancy visit until delivery. All subjects in Group 2 will also use the Share™ technology from the first pregnancy visit until delivery.

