During this visit, pregnant subjects will receive a physical exam, vitals, medical history, demographics, and concomitant medications. Laboratory tests will be performed to assess for A1C. SMBG values will be downloaded. If applicable CGM units and insulin pumps will be downloaded.

Stratification, Visit 2 (Week 1):

Subjects enrolled in the study from pre-conception will be asked to come to clinic as soon as a home pregnancy test or serum blood test confirms pregnancy, during which time routine clinical care will be provided and subjects will be stratified to 1 of 3 study arms based on subject characteristics. Subjects who did not have a pre-conception counseling visit who come to clinic for routine clinical care before 13 weeks of gestation will combine Visit 1 (screening) with Visit 2 (stratification with CGM start). A urine pregnancy test will be administered to confirm pregnancy. Per routine clinical care, we will screen for diabetic neuropathy on physical exam, thyroid disease (TSH blood draw), and kidney disease (24-hour urine protein with creatinine). These tests will be repeated once each trimester. Also per routine clinical care, women will be asked to get a dilated retinal eye exam each trimester and to provide the BDC with a copy of the provider's report of each exam.

Women stratified to Groups 1 and 2 who own a Dexcom G4 or G5 Platinum CGM® will be given 4 sensors. Women stratified to Groups 1 and 2 who do not own a Dexcom G4 or G5 Platinum CGM® will be given Dexcom G4 CGM units, transmitters, and 4 sensors. They will also receive training in the insertion of sensors and CGM use. A Dexcom G4 Platinum® CGM sensor will be inserted that day and will be worn in 7 day periods throughout the study. Although subjects will be asked to wear the device 7 days/week, satisfactory data capture rate is regarded as 5 days of successful CGM readings. The CGM data will be unblinded (real-time use) such that subjects will be able to view glucose values and trends, as well as receive alerts for low and high sensor glucose values. Women will be asked to check SMBG at least 7 times daily (fasting, before meals, 2 hours after a meals, and at bedtime) for the duration of the study.

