Appendix C

Hypoglycemic Fear Survey

Subject ID: _____

Clinic Visit: (dd/mmm/yyyy) : _____ / _____ / _____

Visit (check one): Baseline First Trimester Second Trimester Third Trimester Post-Partum

This survey is intended to find out more about how low blood sugar makes people feel. Please answer the following questions as frankly as possible.

I. Behavior. Below is a list of things people with diabetes sometimes do in order to avoid low blood sugar. Read each item carefully. Circle one of the numbers to the right that best describes what you do during your daily routine to avoid low blood sugar.

	Never	Rarely	Sometimes	Often	Very often
1. Eat large snacks at bedtime	1	2	3	4	5
2. Avoid being alone when my sugar is likely to be low	1	2	3	4	5
3. If test urine, spill a little sugar to be on the safe side. If test blood glucose, run a little high to be on the safe side	1	2	3	4	5
4. Keep my sugar higher when I will be alone for a while	1	2	3	4	5
5. Eat something as soon as I feel the first sign of low blood sugar	1	2	3	4	5
6. Reduce my medication (insulin/pills) when I think my sugar is too low	1	2	3	4	5
7. Keep my blood sugar higher when I plan to be in a long meeting or at a party	1	2	3	4	5
8. Carry fast-acting sugar with me	1	2	3	4	5
9. Avoid a lot of exercise when I think my sugar is low	1	2	3	4	5
10. Check my sugar often when I plan to be in a long meeting or go out to a party	1	2	3	4	5

II. **Worry.** Below is a list of concerns people with diabetes sometimes have. Please read each item carefully (do not skip any). Circle one of the numbers to the right that best describes how often you worry about each item because of low blood sugar.

	Never	Rarely	Sometimes	Often	Very often
11. Not recognizing/realizing I am having a reaction	1	2	3	4	5
12. Not having food, fruit, or juice with me	1	2	3	4	5
13. Feeling dizzy or passing out in public	1	2	3	4	5
14. Having a reaction while asleep	1	2	3	4	5
15. Embarrassing myself or my friends/family in a social situation	1	2	3	4	5
16. Having a reaction while alone	1	2	3	4	5
17. Appearing stupid or drunk	1	2	3	4	5
18. Losing control	1	2	3	4	5
19. No one being around to help me during a reaction	1	2	3	4	5
20. Having a reaction while driving	1	2	3	4	5
21. Making a mistake or having an accident at work	1	2	3	4	5
22. Getting a bad evaluation at work because of something that happens when my sugar is low	1	2	3	4	5
23. Having seizures or convulsions	1	2	3	4	5

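### The plan names two different sources, SMBG profiles and CGM downloads, for its low-glucose indices, and the SMBG profile that the SAP specifies schedules no overnight reading

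*Combined protocol and SAP*

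**What the plan says.** **SAP, measurement sentence.** The Statistical Analysis Plan lists the glucose variability indices, including the percentage "of glucose within/above/below target ranges, J Index, High Blood Glucose Index [HBGI], Low Blood Glucose Index [LBGI"], and says they are measured "throughout pregnancy using the SMBG 7-point profiles for one week taken once per trimester".

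**What the profile contains.** The section on Visits 3 through 13 defines the profile as "blood glucose measurements before meals, 2 hours after meals, and at bedtime". The recording grid in Appendix D agrees: its rows are breakfast, lunch, dinner and bedtime, with a pre-meal (or bedtime) column and a column headed "BLOOD GLUCOSE 2 HOURS AFTER MEAL". The everyday testing request at Visit 2 also names no night test: "Women will be asked to check SMBG at least 7 times daily (fasting, before meals, 2 hours after a meals, and at bedtime".

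**Opening summary.** The primary outcome list draws glucose variability from SMBG data "through log books and downloads as well as CGM downloads and various indices", and attributes J-index, MAGE, HBGI and LBGI to CGM downloads. The same summary plans to analyse CGM data for time below 50, 70 and 80 mg/dl.

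**SAP, modelling sentence.** Later in the same SAP paragraph, repeated SMBG logs and continuous CGM wear are both given as reasons for linear mixed models of variability and of time in, below or above target. It does not say which source supplies which outcome or which between-group contrast.

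**Hypothesis.** The opening summary states that "CGM use will decrease percentage of glucose values below the target range", relative to no CGM. For Share, the stated hypothesis concerns fear of hypoglycemia and severe episodes.

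**The concern.** LBGI is a primary index with two stated sources, and the low-glucose percentage is in much the same position: SMBG in the SAP's measurement sentence, CGM thresholds in the summary. These sources are not interchangeable. CGM covers the night; the scheduled profile stops at bedtime and resumes at the fasting test.

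Night is a plausible place for CGM to act. The device gives low alerts, it is worn continuously, and the trial's own fear survey includes the item "Having a reaction while asleep". An analyst who follows the SAP's measurement sentence would set aside the night hours already recorded in Groups 1 and 2, and would report a below-target percentage that reads as a whole-day figure but reflects mainly waking hours. An effect confined to the night, in either direction, could then go largely unseen, and a null result could be taken to say more about hypoglycemia than the readings support.

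**Working it through.** **1. Count the profile.** From the definition in Visits 3 through 13 and the Appendix D grid:
- 3 pre-meal + 3 post-meal + 1 bedtime = 7 readings a day, which reproduces the plan's seven points.
- 7 × 7 days = 49 per profile week; 49 × 3 trimesters = 147 in pregnancy.
- 3 profile weeks out of 40 = 7.5% of the pregnancy.
- Readings scheduled between bedtime and the fasting test: 0.

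**2. Size of the unsampled interval.** The documents give no bedtime or breakfast hour, so the gap length is an assumption. Share of the day = gap ÷ 24:

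| Assumed gap (h) | Share of day |
|---|---|
| 6 | 25.0% |
| 7 | 29.2% |
| 8 | 33.3% |
| 9 | 37.5% |
| 10 | 41.7% |

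**3. How much low time could lie there.** The rates are assumed, for illustration only: 4% of daytime low and r% of an h-hour night low. Share of all low time falling at night = r·h ÷ [r·h + 4·(24 − h)].
- r = 4, h = 8: 32 ÷ (32 + 64) = 33.3%
- r = 8, h = 8: 64 ÷ (64 + 64) = 50.0%
- r = 12, h = 8: 96 ÷ (96 + 64) = 60.0%
- Extremes over h = 6 to 10: r = 4, h = 6 gives 24 ÷ 96 = 25.0%; r = 12, h = 10 gives 120 ÷ 176 = 68.2%.

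**4. What the profile would show of a change.** Take h = 8, daytime 4%, night 8%. The 24-hour figure is (8 × 8 + 4 × 16) ÷ 24 = 5.33%.
- *All of the effect at night* (8% to 4%, daytime unchanged): the 24-hour figure becomes (4 × 8 + 4 × 16) ÷ 24 = 4.00%, a fall of 1.33 points or 25%. The scheduled profile is expected to show about zero. That follows by construction, so it is the worst case.
- *The same 24-hour fall spread proportionally* (night 8% to 6%, daytime 4% to 3%): (6 × 8 + 3 × 16) ÷ 24 = 4.00%, again a 25% fall. The profile shows 4% to 3%, also 25%.

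The loss therefore depends on how far the night effect differs from the daytime effect, which the documents do not tell us.

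**5. Sources available for each contrast.**
- *Group 1 v Group 2:* both groups wear CGM, so 24-hour data are collected. The recruitment section allows some Group 1 women to use a non-Dexcom CGM.
- *Any contrast with Group 3:* this group has no CGM, and the Control Arm section says the retrospective controls used none throughout pregnancy. SMBG is the only common glucose source. For the retrospective women it comes from meter downloads in the chart; no scheduled 7-point profile is described for them.

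**The case against.** The strongest reply is that the plan already uses CGM. The summary assigns LBGI to CGM downloads and lists CGM time below three thresholds, and the SAP's modelling sentence refers to continuous wear and to time below target, which seven spot readings do not directly measure. This stands to the extent that the SAP does not exclude CGM and that overnight lows can be examined in Groups 1 and 2. It does not settle the matter: the SAP's measurement sentence still assigns the same indices to SMBG, and nothing says which source governs.

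Three stronger readings are tempting, and the documents do not support them.
- A reader might infer that overnight lows cannot be detected at all. A low that persists to the fasting test would be recorded, and meter downloads, which the summary names as a source, may hold unscheduled night tests. The SAP's measurement sentence does not say it uses those downloads.
- A reader might infer that this is the endpoint meant to show that Share reduces lows. Share's stated hypothesis is fear and severe episodes, and under Safety Measures severe episodes are reportable with or without a meter reading; nothing limits them to daytime. The SAP does compare outcomes between Dexcom alone and Dexcom with Share, so these indices enter that contrast, but not as Share's stated target.
- A reader might take one third of each day as a fact of the design. It holds only for an assumed 8-hour gap.

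It is also fair to say that the gap against Group 3 cannot be repaired with the data planned, and that this is a non-randomized pilot without formal power. Both points favour a careful label and a limited conclusion; neither removes the conflict of sources.

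**Conclusion.** The concern holds as a conflict of sources with a measurable consequence. The opening summary and the SAP disagree on where LBGI comes from, and leave the source of the below-target percentage unclear. If the SAP's measurement sentence governs, the interval from bedtime to the fasting test is largely unsampled: 25% to 42% of the day for an assumed gap of 6 to 10 hours. In the illustration, 25% to 68% of low time could fall in that interval, but those rates are assumptions. The effect on a comparison ranges from none, when day and night change in proportion, to a complete miss, when the whole effect is at night.

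For Group 1 v Group 2 the problem can be avoided with data already collected. For contrasts with Group 3 it limits what the hypothesis on percent below target can claim. It should be corrected before analysis; no sample-size figure changes.

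**What to change.** Amend the measurement sentence of the Statistical Analysis Plan so that it agrees with the primary outcome list in the opening summary and names one source per contrast.

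- **Group 1 v Group 2:** compute percent below range and LBGI from 24-hour CGM data. Pre-specify an overnight window (for example 23:00 to 06:00) and report it separately. State how Group 1 women on a non-Dexcom CGM are handled.
- **Any contrast with Group 3:** use SMBG in all arms. Label the result daytime (pre-meal, post-meal, bedtime) percent below range, and limit the conclusion on the CGM versus no CGM hypothesis to waking hours. State how these time points are taken from meter downloads for the retrospective women, and whether unscheduled night readings are left out, with the same rule in every arm.
- **Modelling sentence:** say which source feeds each mixed model.

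The cost is SAP wording and analysis of CGM data already being collected; no visit, device or questionnaire is added. The downsides are that the two kinds of contrast rest on different sources and cannot be read on one scale, and that the claim against no CGM becomes narrower.
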